### 1.5.2 Multiparametric MRI

[figure not shown]
Our group, in collaboration with diagnostic radiologists, has considerable experience with using functional MRI in the routine assessment of prostate cancer prior to definitive therapy, especially prior to radiation therapy. Routine sequences are T2w, T1 non-contrast, T1 DCE-MRI and DWI obtained at 2.5 mm intervals. These sequences are acquired via a 3.0T magnet using a body coil. For the purposes of the studies outlined, MRS will also be performed, but we anticipate that DCE-MRI and DWI-derived ADC maps will be more important sequences in this population.

In **Figure 3** an axial T2w MRI of a male pelvis is shown: resolution  $0.7 \times 0.7 \times 2.5$  mm; Rectangular Field of View:  $360 \times 264$  mm; slice thickness - 2.5 mm (no gap); 72 slices; repetition time (TR) 6300 ms/echo time (TE) 112 ms; flip angle 120°. The arrows point to a hypointense area in the right peripheral zone suspicious for tumor (**Figure 3A**). The prostate, centered in the red box, is presented in the series of T1-weighted gradient echo sequence MR images (**Fig 3B**), acquired with identical spatial resolution, spacing and image size as the T2w MRI. Prior to contrast material injection, one set of MR images were acquired as a pre-contrast image T1 data set. The rest of the data were acquired following intravenous bolus injection of a paramagnetic gadolinium chelate - 0.1 mmol of gadopentetate dimeglumine (Dotarem; Guerbet, Paris, France) per kilogram of body weight. The contrast was administered with a power injector (Spectris; Medrad) at 2.5 mL/s and followed by a 15-mL saline flush. The image sequence parameters were TR/TE 5.1/2.3 ms; flip angle 10°. Eleven post-contrast imaging datasets (34 sec each) were collected. Using DCE-MRI, contrast enhancing lesions are seen in the vast majority of patients; although, little work has been done in men who are candidates for active surveillance, so the proportion of these men who will display enhancing lesions is less certain.

**Figure 4** shows a simple approach that we had adopted in clinical trials involving the targeting of high risk prostate subregions with radiotherapy by combining analyses of the DCE intensity and ADC maps showing the highest region of risk of Gleason score 7 or above, those with high perfusion and low ADC values (dominant lesion), in yellow. Our preliminary biopsy data bear this out; there is a higher risk of Gleason score 7 from dominant regions and a higher risk of Gleason 6 or benign prostate

from non-dominant areas **Figure 5**.

Taking the analysis to another level, we have introduced selectable cutpoints in the in the MP-MRI analyses, as displayed in **Figure 6**. The result is many more defined “habitats” identified, from which targeted MRIs or MRI-directed prostate biopsies will be used to construct probability maps for histopathologic characteristics and gene expression signatures.

## 1.6 Quality of Life

The Quality of Life (QOL) assessment will provide unique data on the effects of MRI monitoring for patients undergoing active surveillance on QOL. We have selected a group of measures that have been used extensively in prostate cancer populations. To assess Health-Related Quality of Life (HRQOL) we will use the SF-12, a short form version of the commonly used SF-36, which is a health survey designed to assess multiple dimensions of HRQOL. The SF-12 captures approximately 85% of the variance in the SF-36 and was developed as a brief measure to address general aspects of quality of life. This brief instrument provides both physical and mental health summary scores. The physical summary score is comprised of physical functioning, role limitations due to physical functioning, bodily pain and general health subscales. The mental summary score is comprised of vitality, social functioning, role limitations due to emotional functioning and mental health subscales. The SF-36 and SF-12 both

demonstrate good internal reliability, with Cronbach's alphas exceeding 0.80. The SF-12 has been used extensively in cancer populations, and has been validated with prostate cancer patients. As an index of Prostate Cancer-Specific Anxiety, we will administer the Memorial Anxiety Scale for Prostate Cancer patients (MAX-PC). The MAX-PC is an 18-item instrument designed to detect symptoms of anxiety in prostate cancer patients. It is designed to evaluate three separate aspects of prostate cancer specific anxiety on 3 subscales: anxiety related to prostate cancer in general (prostate cancer anxiety subscale), anxiety specifically centered around PSA testing (PSA anxiety subscale) and fears of cancer recurrence (fear of recurrence subscale). The MAX-PC9 demonstrated high internal reliability with a Cronbach's alpha of 0.89, with subscale reliabilities between 0.59-0.90 and has been validated in prostate cancer patient samples. Finally, we will evaluate Prostate Cancer-specific Quality of Life. Prostate-specific QOL will be measured with the Expanded Prostate Cancer Index Composite (EPIC-SF12). Development of the EPIC was based on the widely used University of California Los Angeles Prostate Cancer Index and has been used extensively to assess post-treatment related dysfunction among prostate cancer patients. The EPIC has demonstrated excellent reliability (i.e., Cronbach's  $\alpha > .91$ ) across sexual function and sexual bother composites. The EPIC questionnaire will be used to measure changes in QOL over time. For this study, a combined EPIC-SF12 questionnaire will be used. There has been a significant amount of research showing a link between lifestyle modifications pertaining to diet and exercise and improved prostate cancer outcomes. As a result, we would like to collect information on patient's diet and exercise habits to see how changes in these modifiable factors can impact progression on active surveillance. For this purpose we will use the food frequency questionnaire (FFQ). The FFQ forms are optional for the patient and can be refused. All questionnaires will be available in English and Spanish.

## 2. HYPOTHESES

- 1) Multiparametric MRIus-guided or direct MRI-guided biopsies will allow for more directed sampling of the tumors from compartments with distinct MP-MRI characteristics, termed habitats, that will increase the rate of "progression" on early (first and second) surveillance biopsies and decrease the rate of "progression" on late (third and further) surveillance biopsies compared to historic TRUS-guided biopsy rates.
- 2) Identifying higher risk tumor early on will reduce the proportions of patients with poor response to delayed primary treatment
- 3) Radiomics signatures from MP-MRI will define patterns that are associated with progression
- 4) Genomic signatures based on RNA from tumor tissue will define patterns that are associated with habitats and radiomics signatures, as well as progression.

### **3. OBJECTIVES**

#### **3.1 Primary Objective**

To determine if multiparametric MRI and MRI-US fusion biopsies increase the rate of progression (conversion to treatment) within the first two non-diagnostic biopsies after undergoing active surveillance as compared to historical cohorts using standard ultrasound guided biopsies.

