## SCHEMA

### MRI-Guided Active Selection for Treatment of Prostate Cancer: The Miami MAST Trial

- Accrual Goal n = 230
- Primary Endpoint = Rate of progression on the first and second surveillance biopsies

**Figure 1:** Prospective Trial Schema. Patients will have MRI-US fusion biopsy of the prostate within 3 months of study enrollment and then annually thereafter to assess for rate of tumor progression.

MRI – Magnetic Resonance Imaging, PSA – Prostate Specific Antigen, PCA3 – Prostate Cancer Antigen, GLSC – Gleason Score, PPT – Percent Positive Tissue, GGP4 – Gleason Pattern 4 or Above.

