#### **3.3 Exploratory Objectives**

- 1) To define radiomic signatures on multiparametric MRI that select regions of the prostate that are likely to harbor more aggressive disease.
- 2) To molecularly characterize tissue from the multiparametric habitat-directed prostate biopsies and develop genomic signatures of indolent versus progressing prostate cancer using a 1.4 million feature oligonucleotide microarray capable of global high throughput analysis of formalin fixed paraffin embedded specimens.
- 3) To relate radiomics and genomics signatures to existing urine, serum and tissue biomarkers that have been associated with prostate cancer diagnosis and/or progression.
- 4) To determine the incremental benefit of mpMRI, genomic risk testing, and molecular markers at baseline compared to NCCN risk class for predicting reclassification on confirmatory baseline biopsy.
- 5) To evaluate serial changes in mpMRI, genomic risk scores and molecular markers and relate them to progression on active surveillance.

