## 7.2 Evaluations During Intervention\*

- Multiparametric MRI obtained at the University of Miami (+/-) 3 months of enrollment and at 12, 24, and 36 months from initial protocol prostate biopsy.

- MRIus-guided biopsies will be obtained at 0 to 3 months from enrollment (“initial biopsy”) and at 12, 24 and 36 month from initial biopsy.
- History and physical at the discretion of the treating physician. Treating physician can be outside of UM..
- Serum PSA will be done preferably every 6 months or at least once a year up to 36 months from the initial biopsy. If the subject progress, PSA should be done every 6 months (+/- 3 months) or at the discretion of the clinician for the first 3 years and then annually thereafter (+/-6 months) for up to 5 years post treatment.
- If possible, plasma and/or serum (up to 5 tubes) for research purposes (biomarkers) may be obtained at 0 to 3 months from enrollment and at 12, 24, and 36 months from initial biopsy (optional - patient may refuse),
- If possible, post prostate-massage urine (approximately 50 mL) may be collected for research purposes at 0 to 3 months from enrollment and at 12, 24, and 36 months from initial biopsy (optional - patient may refuse). Urine research collection will not be done if research funds are not available.
- Quality of Life surveys obtained 0 to 3 months after enrollment and every 12 months from initial biopsy:
  - Expanded Prostate Cancer Index Composite Questionnaire (EPIC+SF12)
  - Memorial Anxiety Scale for Prostate Cancer patients (MAX-PC)
  - Optional - Food Frequency Questionnaire (FFQ) will be collected only atbaseline.

*\* Follow-up evaluations and visits may occur  $\pm$  1.5 months around each scheduled 6-month timepoint. For example, for the 6 month follow-up, the patient may be seen anytime between 4.5 and 7.5 months from the time of the first prostate biopsy. For the 12-month follow-up, the patient may be biopsied between 10.5 and 13.5 months from the time of the first prostate biopsy. Since the first biopsy may be from between 0-6 months from the day the patient is enrolled, each subsequent calendar event is timed in reference to the time of that first biopsy.*

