#### *10.3.3 Area under ROC curves as predictive measure and incremental prediction improvement for progression on baseline biopsy.*

Patients will be categorized at baseline by NCCN risk class ranging from very low risk to intermediate risk and into those who progressed on the baseline biopsy and those who did not. Logistic regression will be used to model the association between NCCN risk class and progression using AUC for ROC curves. The incremental benefit of mpMRI, genomic testing and molecular markers compared to NCCN risk alone will be evaluated by comparing AUC using a likelihood ratio test. MRI will be categorized from 1-5 using PIRADS, while genomic test scores and molecular markers can be used as continuous scores or categorized into levels of risk (low/ intermediate/high).

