## 10.5 Statistical Analysis

Descriptive statistics will be done for patient demographics and baseline disease characteristics. Counts and percentages will be used to summarize the distribution of categorical variables while median, range, mean and standard deviation will be used for continuous variables. Baseline characteristics will include age, race/ethnicity, T-stage, Gleason score, PSA, PSAD and performance status. Continuous scores will be compared using ANOVA and linear regression controlling for common demographic and clinical variables.

For each scheduled surveillance biopsy session, we will tabulate patients and the following status categories: biopsy indicating progression, biopsy negative for progression, biopsy not performed for progression detected on earlier biopsy, biopsy not performed because patient refused, or biopsy not performed because patient dropped out of study.

Time to event endpoints such as progression and BCR will be analyzed by Kaplan-Meier (KM) or competing risk (CR) methods. Where the Kaplan Meier method is used, point estimates and two-sided 95% confidence intervals for rates will be reported for selected times using Greenwood's variance and the log-log transform method. Median survival time, if attained, will also be reported. We will report the progression rate and the cumulative progression rate for each surveillance biopsy. Taking the third scheduled biopsy at the end of 2 years as illustration, the progression rate at 24 months is the proportion of biopsied patients indicating progression among the total number of biopsied patients over the 24 month period. The 24-month cumulative progression rate is the primary endpoint, which will include those who complete the first three biopsies or have progression from the first or second biopsy. The primary endpoint, 24-month cumulative progression rate, will be estimated and reported with corresponding 95% confidence intervals. Groups will be compared by the log rank test. In addition, we will report and plot the cumulative progression rates in each arm for the four scheduled surveillance biopsies. It is expected that the early difference with historical values and those obtained with MRI-guided biopsies will not be sustained; that is, the 36-month cumulative progression rates will be approximately equal. Similar estimation of time-specific and cumulative rates will be done for Histological progression.

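### The sections describing the primary endpoint disagree on biopsies and events, and the 12.5% null, labelled a 24-month cumulative rate, is unsourced and below what the plan's own per-biopsy rates cumulate to

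*Combined protocol and SAP*

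**What the plan says.** **Biopsies.** Section 7.2 schedules an initial biopsy at 0 to 3 months from enrollment "and at 12, 24 and 36 month from initial biopsy". The diagnostic biopsy precedes enrollment (Appendix II).

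- Schema: "Primary Endpoint = Rate of progression on the first and second surveillance biopsies".
- Section 2, hypothesis 1: more progression on the first and second surveillance biopsies, and less on the third and later ones.
- Section 3.1: the effect is to "increase the rate of progression (conversion to treatment) within the first two non-diagnostic biopsies after undergoing active surveillance".
- Section 3.3 treats the initial biopsy as a baseline, with an objective "for predicting reclassification on confirmatory baseline biopsy". Section 10.3.3 divides men "into those who progressed on the baseline biopsy and those who did not".
- Section 10.5 makes the 24-month biopsy the third scheduled one. It defines the 24-month cumulative rate as one "which will include those who complete the first three biopsies or have progression from the first or second biopsy", and adds that "we will report and plot the cumulative progression rates in each arm for the four scheduled surveillance biopsies".

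**Event.** Section 3.1 equates progression with conversion to treatment. The opening of section 10 says biopsy criteria. Section 10.1.1 lists four histological criteria and, as item (v), any treatment whatever the histology. Section 10.1.2 defines histological progression separately, without (v).

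**Null.** Section 10.4 tests 12.5% against 25% with 150 patients, a two-sided 5% binomial test and 97.3% power. It calls 12.5% the historical 24-month cumulative expectation and cites nothing.

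**The concern.** The trial has no concurrent control, so the primary comparison sets one observed proportion against one historical figure. That works only if both count the same event over the same biopsies. MRI targeting is expected to reveal missed tumor early (sections 1.2 and 1.5.1), so the initial biopsy matters to the count, as does counting treatment without histological progression. If the 12.5% refers to fewer biopsies or a narrower event than section 10 counts, the test can report an MRI effect that is only a mismatch of definitions.

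**Working it through.** **1. Biopsy set.** Numbering the protocol biopsies 1 (initial), 2 (12 months), 3 (24 months) and 4 (36 months):

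- Section 10.5, with 7.2: biopsies 1 to 3. Progression on the initial biopsy counts.
- Section 3.1, read literally: biopsies 1 and 2, because only the pre-enrollment biopsy is diagnostic.
- Schema: biopsies 2 and 3 if the initial biopsy is a baseline (3.3), or 1 and 2 under 10.5's count of four surveillance biopsies.
- Hypothesis 1: under 10.5's numbering, biopsy 3 is late, where a decrease is expected, yet it lies inside an endpoint meant to show an increase.

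**2. Event and denominator.** The denominator in 10.1.1 and 10.5 is men with all planned biopsies to date, or with an earlier biopsy showing progression. A man treated without biopsy progression before his 24-month biopsy is an event under (v). Read literally, he is in neither denominator group. Nor does he have a status category in 10.5: its reasons for a missing biopsy are earlier progression and "biopsy not performed because patient refused, or biopsy not performed because patient dropped out of study".

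**3. The stated power.** Exact binomial, n = 150, at most 0.025 in the upper tail. With p = 0.125, P(X ≥ 28) = 0.0193, so the rule is to reject at 28 or more. With p = 0.25, P(X ≥ 28) = 0.9734. The plan's 97.3% is reproduced.

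**4. Where 12.5% might come from.** Section 1.5.1 gives progression of 7%, 18% and 17% at the first, second and third surveillance biopsies.

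- Simple mean of the first two: (7 + 18)/2 = 12.5%.
- Cumulated over two biopsies, if the 18% is conditional on no earlier progression: 1 − 0.93 × 0.82 = 23.7%.
- If the 18% is already cumulative: 18%.
- Cumulated over three biopsies on the conditional reading: 1 − 0.93 × 0.82 × 0.83 = 36.7%. This only shows that the number of biopsies matters. The historical biopsy timing is not given.

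**5. Consequence of a different historical rate, n = 150.** The second column is P(X ≥ 28) at that rate. The last two columns make that rate the null.

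| Matching historical rate | Increase declared although MRI changes nothing | Cut-off against this null | Power at a true 25% |
|---|---|---|---|
| 12.5% | 1.9% | 28 | 97.3% |
| 15% | 12.8% | 32 | 87.2% |
| 18% | 44.9% | 37 | 56.9% |
| 20% | 69.0% | 41 | 28.2% |
| 23.7% | 94.3% | 47 | 4.7% |

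**The case against.** **Section 10 governs.** A reader might infer that it is undecided whether progression on the initial biopsy counts. The documents do not support that: 10.1.1 and 10.5, with the schedule in 7.2, count it. The conflict with the schema, hypothesis 1, 3.1 and the opening of section 10 remains, and the historical rate could have been matched to any of these descriptions.

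**Criterion (v) may be only awkward drafting.** The lead-in to 10.1.1 lists treatment among the things a biopsy can indicate, so treated men might be meant to enter the denominator. That reading is possible, and one sentence would settle it. Section 10.5 also offers Kaplan-Meier or competing-risk methods and reports histological progression separately.

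**The historical figures are not like for like.** A reader might infer that 12.5% is refuted by 64/249 = 26% at mean follow-up 2.9 years (1.5.1), about 30% at median 3 years (1.4.1) and nearly a third within three years (1.1). It is not. These are roughly three-year figures from cohorts whose entry criteria and events differ or are not matched to this trial, so they are only supportive. Scaling them to 24 months would need a constant hazard, which sits badly with 7% followed by 18%.

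**The origin of 12.5% is inferred.** The match with the mean of 7% and 18% is exact, but the documents do not say that this is how it arose.

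**The binomial test appears only in 10.4.** Section 10.5 speaks of 95% confidence intervals and a log-rank test. So the error rates hold if the 10.4 test is applied. An exact 95% interval read against 12.5% would give the same decision.

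**The accrual goal is 230, not 150.** With 207 analysed (230 × 0.9, applying the 10% dropout as an assumption), power against a 15% null is 95.3% rather than 87.2%. However, the chance of a false increase at a 15% historical rate rises from 12.8% to 14.5%. This is a reason to restate power at the number to be analysed.

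**Conclusion.** The point holds. Section 10 has an operative endpoint, but the schema, hypothesis 1, section 3.1 and the opening of section 10 do not describe the same one. The treatment criterion and the denominator do not fit together as written. The arithmetic of 10.4 is right; the weakness is the 12.5% input, which is uncited and below either reading of the rates in 1.5.1 (18% or 23.7%). The exact match with their mean suggests a per-biopsy average used as a cumulative rate.

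The size depends on the unknown matching rate: a false declaration of increase in 12.8% of trials at 15%, rising to 94% at 23.7%, against 2.5% intended in that tail. A reader might infer that the trial will very probably give a false positive. The documents do not support that. The 94% needs the conditional reading of the 18%, comparable biopsy timing and comparable entry criteria, and the historical cohort's entry criteria were stricter. So 12.5% cannot be strictly excluded. The textual conflicts rest on no such assumption.

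**What to change.** 1. Number the protocol biopsies once. Use one biopsy set and one event definition in the schema, section 2, section 3.1, the opening of section 10, 10.1.1 and 10.5, and say outright whether progression on the initial biopsy counts.
2. Derive the null as a cumulative rate from a named historical cohort with the same event and the same number of biopsies or time window. Cite the source and show the derivation in 10.4. If 12.5% has such a source, stating it settles this part.
3. Restate null, alternative and power at the number to be analysed, without enrolling more men.
4. Unless the historical rate also counts elective treatment, make the historical comparison on the histological progression already defined in 10.1.2.
5. State that men treated without histological progression enter the denominator and how they are counted, and add a status category for them in 10.5.

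The cost is wording changes and one derivation from existing data; section 4 refers to an active surveillance database. No new trial data are needed. The downside is that the 97.3% power will probably fall. At n = 150, 90% power would need a true trial rate of about 26%, 29%, 32% or 36% against a null of 15%, 18%, 20% or 23.7%.

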#### **3.2 Secondary Objectives**

- 1) To identify whether earlier identification of progression with MRI and MRI-US fusion biopsy will portend improved outcomes of patients undergoing delayed primary surgery or radiation after initial surveillance at the University of Miami
- 2) To determine the effect of multiparametric MRI and MRI-US fusion biopsy on health related quality of life and cancer specific anxiety using patient reported validated questionnaires.
- 3) To determine the incremental benefit of mpMRI, genomic risk test, and molecular marker at baseline compared to NCCN risk class for predicting progression on Active Surveillance

